9.1 Data Collection..... 23

9.1.1 Source Data 24

9.1.2 Data Capture and Storage 25

9.2 Record Retention 25

10. CAS OVERSIGHT 26

10.1 Governance structure 26

10.2 Quality Control and Quality Assurance 26

11. ETHICS AND DISSEMINATION 26

11.1 Modifications to the protocol 27

11.2 Protocol Deviations 27

11.3 Confidentiality 27

11.4 Participant Reimbursement 28

11.5 Financial Disclosure and Conflicts of Interest 28

11.6 Dissemination and translation plan 28

12. APPENDICES 28

RTI Release

PROTOCOL SYNOPSIS

Title	EPIDIOLEX® CAS: A Compassionate Access Scheme (CAS) of an investigational Purified Cannabidiol Oral Solution (Epidiolex®) in paediatric patients with severe refractory epilepsy
Objectives	The objective is to delineate a protocol for the provision and safety monitoring of a compassionate access scheme. CAN-1 is not a clinical trial and therefore no clinical research questions are defined.
Design	A compassionate access scheme to provide an investigational product to a group of children with severe epilepsy.
Outcomes	Safety monitoring of adverse events and limited efficacy data
Study Duration	Until Epidiolex® is TGA registered in Australia or until no longer available
Interventions	Safety monitoring including regular scheduled clinical review and blood monitoring of adverse events
Number Of Participants	30 patient doses at any given point in time
Population	Children (2 to 18 years of age) with intractable epilepsy not suitable for inclusion in a standard clinical trial. Because some patients are expected to discontinue use (e.g. condition worsens), the total number of patients to be treated under this CAS is unknown.

GLOSSARY OF ABBREVIATIONS

Abbreviation	Term
AE	Adverse Event
AED	Anti-epilepsy drug
AP	Authorised Prescriber
CAS	Compassionate Access Scheme
CBD	Cannabidiol
CHQHHS	Children's Health Queensland Hospital and Health Service
HREC	Human Research Ethics Committee
MoU	Memorandum of Understanding
PISCF	Patient Information Sheet Consent Form
PO	CHQHHS Clinical Cannabis Project Office

1.2. Expected duration

Until Epidiolex[®] is TGA registered in Australia or until no longer available.

2. INTRODUCTION

2.1. Background and rationale

Epidiolex[®] is expected to become the first pharmaceutical-grade (e.g.: GMP manufactured) cannabis product made available in Australia for the treatment of refractory paediatric epilepsy. Due to the age and co-morbid health issues of this patient population, pharmaceutical-grade rather than uncontrolled "street" or "food-grade" products are necessary to ensure and provide the necessary consistency and strength.

Though currently an unapproved product, both locally and internationally, Epidiolex[®] is currently undergoing Phase 3 trials in the treatment of Lennox-Gastaut, Dravet Syndromes and Tuberous Sclerosis syndromes around the world. These trials are expected to be completed in 2016, with NDA submission to follow soon after. In addition, there is an emerging body of both pre-clinical and clinical safety data; the latter predominantly from Expanded Access Programmes and open-labelled studies.

There has not been any randomised placebo controlled clinical trials performed to date that involve giving Epidiolex[®] to children under 2 year of age. One open-labelled interventional

trial enrolling 214 participants from age 1 to 65 years with severe epilepsy have received CBD oral solution (Epidiolex[®]), however, this has not been within a formal clinical study (there was no placebo or 'dummy' treatment). On average, monthly seizure frequency was reduced by approximately a third (36%) in this group (Devinsky et al, 2015).¹

The supply of Epidiolex[®] for a series of clinical activities was negotiated between the Queensland Government and the manufacturer, GW Pharmaceuticals. These activities were formalised in a Memorandum of Understanding (MoU); one of these being a Compassionate Access Scheme (CAS) enabling access to Epidiolex[®] for up to 30 patients at any one time. This treatment option is provided to children who suffer from severe epilepsy and are unable to participate in clinical trials.

GW Pharmaceuticals intends to provide ongoing supply of Epidiolex[®] in accordance with this protocol and related agreements until such time that the Australian Therapeutic Goods Administration (TGA) approves a marketing authorisation application for the product, (e.g. Epidiolex[®] is placed on the Australian Register of Therapeutic Goods) or until the product is no longer available.

2.2. Aim(s)

Primary Aim

1) To prescribe Epidiolex[®] as an anticonvulsant for a group of 30 eligible children (2 to 18 years) at any one time with severe refractory epilepsy.

Secondary Aim

2) To provide paediatric neurologists with the experience of prescribing and managing Epidiolex[®].

3. OBJECTIVES

CAN-1 is not a clinical trial and therefore no clinical research questions are defined.

The objective is to delineate a protocol for the provision and safety monitoring of a compassionate access scheme. The scope of data collected is the same as in other GW Pharmaceuticals Epidiolex[®] Expanded Access Programs around the world. A secondary purpose of the data collection is to allow evaluation of the safety data in an Australian population.

¹ Devinsky, O, et al. 2015. 'Cannabidiol in patients with treatment-resistant epilepsy: an open-label interventional trial', *The Lancet Neurology*, vol. 15, no. 3, pp. 270-278.

4. DESIGN

4.1 Type

CAN-1 is a Compassionate Access Scheme designed to provide access to Epidiolex[®] to a maximum of 30 eligible paediatric patients (at any one time).

Epidiolex[®] will be prescribed by physicians endorsed by the TGA under the Authorised Prescriber scheme. Paediatric neurologists with an appointment at any QLD Public Health Organisation are invited by the CHQHHS Clinical Cannabis Project Office (PO) to submit an application to participate in CAN-1. The PO will assist the clinician where they meet the criteria prescribed in this protocol to obtain Authorised Prescriber status via the required application to their institutional HREC and then to the TGA.

Due to the limited supply of Epidiolex[®] at any given time, approval of an AP does not necessarily guarantee the inclusion of their patients in the CAS, but rather enables them to make application to the PO for consideration of eligibility. Further information concerning inclusion on the CAS is provided at Section 5.2.1 below.

Application to the PO will be made after the AP/Paediatric Neurologist contacts the patient and obtains verbal consent to release certain health information to the PO. This de-identified information, linked to the patient's file via unique identifier, will be used by the PO to rank the patient and determine suitability for inclusion in the CAS. Consent will be noted in the patient's file.

If the PO approves a request, the AP will be notified at which time they would schedule a screening visit with patient/parent. During this visit, the AP will review the Patient Information Sheet and Informed Consent Form (PISCF) with the patient/parent and address any questions. If the patient/parent voluntarily consents, the patient's eligibility will be reviewed, and if confirmed eligible, would be provided an initial prescription for up to 3 months of Epidiolex[®]. A site-based coordinator will be scheduled to facilitate during this enrolment process.

Upon review of a successfully completed informed consent form, the PO will provide the appropriate hospital pharmacy with the patient's unique identifier or authorization code, DOB and AP name. This information will also be present on the script. The pharmacy will only dispense the product once the unique identifier, DOB, and informed consent have been confirmed by the PO.

PO personnel will be available to Authorised Prescribers to assist in recruitment, screening, baseline and monthly telephone review and quarterly clinical visits. As well, the Project Office will be available to provide educational and logistical support to the APs so long as the CAS is in effect.

4.2 Sites

- Lady Cilento Children's Hospital

4.3 Education of Authorised Prescribers

All APs will be required to attend an educational session facilitated by the PO ahead of prescribing Epidiolex®. This education session will cover:

- The responsibilities and obligations of the AP
- The recruitment process, including key eligibility criteria and the informed consent procedure.
- Mandatory safety reporting
- Patient monitoring, data collection and reporting.

Attendance will be recorded in a training log.

5. PARTICIPANTS AND RECRUITMENT

5.1 Number of Participants

A maximum of thirty (30) patients may access this product at any given time. With replacements possible, the total sample size is unknown.

5.2 Eligibility Criteria

Participants will be assessed initially by the Authorised Prescriber for eligibility using a set of predetermined objective criteria as defined in Section 5.2.1 below. Where the patient meets the inclusion criteria, and does not meet the exclusion criteria, their suitability to receive product is based on their ranking against all other applicants based on the total number of non-elective, epilepsy-related hospital admissions in 2016. A second tier of ranking based on younger patients having higher priority may be required.

5.2.1 Inclusion Criteria

Potential patients for inclusion on the CAS must meet ALL of the following:

- Have a clinical diagnosis of severe, intractable childhood epilepsy.
- Be 2 to 18 years of age at the time of consent.
- Experience seizures at least daily for the past six months.
- Have had at least one non-elective epilepsy related hospital admission during 2016. This does not include elective admissions such as epilepsy related investigations or initiation of the ketogenic diet.
- Failure of a clinical trial of at least five anti-convulsant drugs, including one trial of a

combination of two drugs. Vagal nerve stimulation, epilepsy surgery, deep brain stimulation, or ketogenic diet are considered equivalent to a trial of an anti-convulsant drug for the purpose of this inclusion criteria.

- Attempted and failed² an appropriate anticonvulsant where specifically indicated for genetic epilepsy syndromes (e.g. Stiripentol in Dravet syndrome, Vigabatrin for TSC, etc.)
- The dominant seizure type being uncountable, i.e. not suitable for a typical randomized clinical anti-convulsant trial; for example, atypical absence, non-convulsive status, multiple tonic seizure cluster, large number of daily seizures
- Being administered between 1 and 4 baseline anti-epileptic drugs at stable doses for a minimum of 4 weeks prior to enrolment. Vagus nerve stimulator (VNS) and ketogenic diet do not count toward this limit.
- Verbal consent to have certain health information used in determining patient suitability to participate in the CAS.
- Written informed consent obtained from the patient or the patient's parent/guardian.
- Parental/guardian compliance to CAS monitoring requirements including regular blood testing and safety data collection and storage.

5.2.2 Exclusion criteria

Patients who meet any of the following criteria are not eligible for participation:

- Pre-existing abnormalities of complete blood count, electrolytes, coagulation, hepatic function or enzymes that are considered clinically significant as judged by the Authorised Prescriber (e.g. WBC < 4, Platelets < 60000, ANC < 1.5, ALT or AST > 2 times upper limit of normal)
- Clinically significant ECG abnormalities (e.g. QTc > 460 msec, PR > 0.2 sec, QRS > 0.1 sec)
- Have a terminal illness, with life expectancy not longer than 3 months.
- Use of any cannabis-related product in the month prior to consent
- Female subjects who are pregnant will be excluded. Cannabidiol is contraindicated in pregnancy. If a female subject is able to become pregnant, she will require a negative serum pregnancy test before entry into the scheme. Female subjects will be informed not to become pregnant while taking cannabidiol. Female subjects must inform the investigator and consult an obstetrician or maternal-fetal specialist if they become pregnant during the study.
- Known allergy to CBD or any cannabinoid or any component of Epidiolex[®].

5.3 Identification of potential participants

To identify potential participants, the neurologist will review their patient records and, where they believe the patient meets eligibility criteria, contact the patient and seek verbal consent to provide DOB and number of 2016 hospitalisations to the PO for the purposes of

² "failed to respond" is defined as either partial or full failed response to anticonvulsant medication

prescreening. Where obtained, consent will be documented in the patient's medical record.

The initial recruitment of patients will be staged over six months and will be ongoing with 30 patients being eligible at any one time.

A registry of eligible patients will be established and held by the PO and used to determine which patients are invited for a screening visit and which remain on the waiting list. This process is ongoing, in that additional, eligible patients can be notified to the PO at any time.

5.4 Consent

Consent will involve a two-step process. Initially, verbal consent will be obtained prior to forwarding DOB and number of hospital admissions to the PO. (See Section 5.3). Consent will be recorded in the patient file.

Patients who are objectively deemed suitable for inclusion in the CAS will be invited for a screening visit. At this meeting and before any CAS procedures are conducted, patients will be provided with a Patient Information Sheet and asked to provide their consent for screening as well as, if deemed eligible, for the purpose of ongoing monitoring and data collection activities. (PISCF, Appendix 1).

Given the age and the severe medical condition of patients, a parent or legal guardian will be required to provide written consent on their behalf. The AP will countersign the consent form acknowledging the information that has been discussed. The patient will be given a copy of the PISCF to retain and a copy kept of the patient's medical records.

5.5 Dispensing process

The Epidiolex[®] product will be dispensed only by pharmacies within QH facilities, including:

- Lady Cilento Children's Hospital

Dosing Guidelines may be reviewed with the patient and caregiver by the hospital pharmacy (Appendix 2).

The PO will provide the appropriate pharmacy the list of unique identifiers, corresponding DOBs and name of the Authorised Prescriber for each patient enrolled in the CAS. The pharmacies will crosscheck this information with that provided on the prescription. Only if the information matches may the product be dispensed.

Hospital pharmacies will dispense the prescription directly to the patient, the patient's parent or guardian, or authorised recipient. The product may not be couriered to a local pharmacy for dispensing.

6. INTERVENTION

6.1 Product Information

Trade name: Epidiolex[®]

6.1.1 Route of administration and dosage

Route of administration:

Epidiolex[®] oral solution 100 mg/ml will be administered orally or via peg tube.

Dose / titration schedule:

Initiation of treatment will begin with 5 mg/kg/day CBD given in two divided doses. The dose will be increased by 5 mg/kg/day at a minimum of every seven days up to a maximum dose of 25 mg/kg/day given in two divided doses with the aim of arriving at an optimal dose with regards to safety and tolerability.

Doses of concomitant antiepileptic drugs may be altered and recorded during this study if necessary.

6.1.2 Dose modification

The Authorised Prescriber has the discretion to modify the dose within the parameters of the schedule above. This means if there is efficacy demonstrated the dose does not need to be increased. Conversely if side effects emerge such as drowsiness, reducing either Epidiolex[®] or concomitant medications is acceptable as per the Authorised Prescriber's usual practice.

Doses greater than the recommended 25mg/kg/day are not to be used. Any further escalation

in dose would require a protocol amendment following agreement between GW Pharmaceuticals and CHQHHS.

6.1.3 Preparation and administration of study drug

The patient or parent/guardian, via plastic syringe, administers Epidiolex[®] orally (see Appendix 2) or via peg tubing (see Appendix 7). The AP and/or Pharmacist may assist in selecting the appropriate size syringe for giving the patient's dose regime, if needed.

Syringes can be used more than once but care should be taken that the syringe is completely dry prior to placing it into the bottle. Moisture may cause the solution to turn cloudy.

The product shelf life is 18 months. The expiry date is provided on the label. Once opened the product may be used for no more than 28 days, after which any remaining amount must be discarded.

Do not store product above 30°C. Do not refrigerate or freeze. Keep away from heat and direct sunlight.

See Appendix 2 for Dosing Instructions.

6.1.4 Dispensing and product accountability

At the inception of the CAS, the PO will review the expected demand and ensure adequate stock is available at each participating hospital pharmacy. Product is ordered (from the depot) by Head of Hospital Pharmacy or delegate. The depot keeps a delegations log of persons authorised to place an order.

The pharmacy will receive from the project office the names of all Authorised Prescribers as well as eligible patient's DOB and identifier. In order to dispense the product, the pharmacist must review & confirm the script, which will include the AP's name, patient's DOB and associated identifier.

The Pharmacy will maintain accurate records of the date and amount of product received from the depot, and what has been dispensed. The PO is authorised to request an Epidiolex[®] stock reconciliation from the pharmacy at any time.

Patients are asked to return the product to the pharmacy where the product was dispensed if any drug is remaining after 28 days of opening bottle, where it will be disposed.

6.1.5 Excluded medications and treatments

The participant is not eligible if a cannabinoid has been used in the month prior to consent. There are no other excluded medications.

Patients are advised not to take any cannabis-related products in conjunction with Epidiolex[®] as this may create a risk of inappropriate and uncontrolled dosing of cannabinoids. No more than 4 anticonvulsant medications in total are allowed to be concurrently prescribed as per the eligibility criteria.

In vitro, CBD is an inducer and inhibitor of selected liver enzymes CYP450 and UGT. Whether *in vivo* there is a clinical consequence of this is still under investigation. It is advised that careful titration of CBD be undertaken in those patients taking concomitant medications metabolised by these liver enzymes. Ongoing phase 3 studies are addressing this question directly.

7. CAS VISITS AND PROCEDURES

Once enrolled, participants are required to comply with monitoring requirements that take place both on a routine schedule and during unscheduled visits.

If under uncontrolled circumstances the participant is unable to perform a physical visit to the institution to complete a procedure outlined in the protocol (e.g. blood test), the institution can request a waiver and upon approval by the PO have the procedures completed at a local site. This does not mean that Epidiolex[®] can be dispensed at the local site. Epidiolex[®] can only be dispensed by an approved AP pharmacy and only by a pharmacist delegated to dispense Epidiolex[®].

The following data will be collected during monitoring:

- Seizure types
- Seizure Intensity or duration (week 4 onwards):
 - “Increased” (I) or “Decreased” (D) or No change (N)
- Body Weight
- Seizure Types
- Number of:
 - Days Rescue Medication was Used (in last 28 days)
 - Episodes of Status Epilepticus (SE) in the last 28 days, both convulsive and non-convulsive
 - Emergency Room (ER) visits in the last 28 days
 - Hospitalisations in the last 28 days
- Epidiolex[®] and Concomitant AEDs:
 - Dose
 - Plasma level (AED only)
- Biochemistry and Full Blood Count (FBC)
 - Na⁺
 - K⁺

- Cl-
- HCO₃
- BUN
- Creatinine
- RBC
- HCT
- HGB
- MCV
- MHC
- MCHC
- WBC and differential
- Platelets
- Liver Function Tests (LFT)
 - AST
 - ALT
 - Albumin
 - Total bilirubin
 - Gamma-glutamyl transferase (GGT)
 - Alkaline phosphatase (AP)
 - INR

For any clinically significant (> 3 x ULN) elevation of ALT or AST in patients being treated with Epidiolex[®], the following laboratory measures, at minimum, should be assessed within 72 hours: repeat ALT/AST, total bilirubin, alkaline phosphatase, and GGT.

All CAS participants with elevated LFTs should be followed until all abnormalities return to the baseline state as assessed by the AP with AST/ALT < 3X ULN. Please refer to section 7.8.1 for LFT abnormality criteria as a reason for withdrawal from the study.

- 24 hour Video EEG
- Serum Pregnancy Test (in all females of reproductive age)
- ECG
- Global Impression of Change (measured by patient/parent, and separately physician)
- Adverse Events
 - Diagnosis, syndrome, signs, symptoms
 - Severity
 - Plausible relationship to CAS medication
 - Action taken with CAS medication
 - Other action taken (if any)
 - Outcome
 - Serious adverse event (if yes, then reason for seriousness)
 - Start and Stop date

- Duration if <24hrs
- Epidiolex[®] dose

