7.1 Monitoring Schedule

Data will be collected at Screening, Baseline, Monthly Phone follow up, Quarterly visits, Withdrawal visit, Unscheduled visits, Participant withdrawal and at CAS closure and the detailed below. See Appendix 3 for a complete Monitoring Schedule.

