7.4 Monthly Phone Follow-up

Monitoring activities may be conducted via phone at 4 weeks and 8 weeks after the baseline, or quarterly in-person visits. A study coordinator will make the calls and record the relevant information. Section 9, Data Management, describes the recording and management requirements for this information.

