7.7 Unscheduled visit

The AP is required to notify the project office if there is an unscheduled visit. Details of the reason for the visit, any adverse events, and blood tests would need to be documented and forwarded to the project office. If the visit is due to an Adverse Event or a Serious Adverse Event, then all procedures described in Section 8, Adverse Events and Risks, will be followed.

At a minimum, weight & height, FBC, EUC, LFT, AED plasma levels will be measured and recorded.

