7.8 Participant Withdrawal

7.8.1 Reasons for withdrawal

Patients are free to withdraw from the study at any time upon their request or the request of their legally acceptable representative. Withdrawing from the study will not affect their access to standard treatment or their relationship with the hospital and affiliated health care professionals.

The patient must be withdrawn from the CAS if any of the following events occur:

- The patient experiences an Adverse Event or Serious Adverse Event which in the opinion of the AP would compromise the continued safe participation of the patient in the CAS
- Develops, during the course of the study, symptoms or conditions listed in the exclusion criteria
- The patient becomes pregnant, as evidenced via a positive pregnancy test
- The patient is unwilling or unable to continue, or the parent/legal representative is unwilling or unable to allow the patient to continue
- The AP decides that withdrawal is in the patient's best interests
- ALT or AST >8xULN
- ALT or AST >5xULN for more than 2 weeks
- ALT or AST >3xULN and (TBL >2xULN or INR >1.5)
- ALT or AST >3xULN with the appearance of fatigue, nausea, vomiting, right upper quadrant pain or tenderness, fever, rash, and/or eosinophilia (>5%)

All patients with elevated LFTs should be followed until all abnormalities return to the baseline state as assessed by the investigator with AST/ALT < 3X ULN.

The Authorised Prescriber may withdraw a patient from the CAS if the patient:

- Does not fulfil the monitoring requirements
- Shows an increase, or no measureable improvement, in seizure frequency and/or severity as assessed by the AP.

The Authorised Prescriber will also withdraw all participants if the CAS is terminated either

due to Epidiolex[®] being registered by the TGA, or in the event GW Pharmaceuticals ceases to supply product.

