9.1.1 Source Data

Table 9.1: Summary of Source and Secondary Data

Type	template	Source data format	Stored in Hospital CAS file (hardcopy)	Recorded in spreadsheet	Excel	Time points	Comments
Informed consent	CAN-1: PISCF	hardcopy	yes	tick-box to completion	verify	recruitment	
Lab results	n/a	PowerChart	yes	yes		Screening, monthly, quarterly, unscheduled	
Script	CAN-1: Script template	hardcopy	yes	yes		Initial, as needed	
AEs	CAN-1: AE report	Hardcopy	yes	yes		Monthly, as needed	
SAEs	GW SAE- Australia Form	Hardcopy	yes	yes		As needed	
	CHQHHS-HREC	On-line	yes	Only date of submission			
	ADRAC "blue card"	Hardcopy	yes	Only date of submission			
non-lab data	GW Pharmaceuticals monthly monitoring form	hardcopy	No (TBC)	yes		Screening, monthly, quarterly, unscheduled	

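### The minimum 72-hour repeat panel after ALT/AST >3xULN omits INR and the WBC differential, so a blood-only repeat leaves one limb of each of two mandatory withdrawal rules unjudged

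*Protocol*

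**What the plan says.** **The repeat panel.** Section 7 sets the work-up for an ALT or AST above 3xULN: "the following laboratory measures, at minimum, should be assessed within 72 hours: repeat ALT/AST, total bilirubin, alkaline phosphatase, and GGT". The next paragraph asks for follow-up until the abnormalities resolve and refers the reader to 7.8.1 for the liver criteria for withdrawal.

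**The withdrawal rules.** Section 7.8.1 has four liver rules, each mandatory. Two depend on ALT/AST alone: above 8xULN, and above 5xULN for more than 2 weeks. The other two start at 3xULN and need something further:

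- The third rule is "ALT or AST >3xULN and (TBL >2xULN or INR >1.5", where the bracket closes.
- The fourth combines ALT or AST above 3xULN with a list of signs that starts with fatigue, nausea and vomiting and ends with "right upper quadrant pain or tenderness, fever, rash, and/or eosinophilia (>5" per cent.

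**Other places that bear on the repeat.** The routine list in Section 7 has INR under liver function tests and the WBC differential with the full blood count. Section 7.7 says of an unscheduled visit: "At a minimum, weight & height, FBC, EUC, LFT, AED plasma levels will be measured and recorded". Section 7 also lets a participant who cannot attend, under a waiver and "upon approval by the PO have the procedures completed at a local site".

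**The concern.** The panel and the two compound rules start at the same threshold, and the text links one to the other, so the panel should supply what the rules need. It does so only in part. It names ALP and GGT, which no withdrawal rule uses, and leaves out INR and the differential, which two mandatory rules do use.

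A site that draws exactly the named tests has done all that the sentence asks. Section 10.2 has Project Office staff check compliance with protocol requirements, and against that sentence they would find nothing missing. Yet neither INR nor the eosinophil percentage could be judged on the repeat sample.

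This matters for a patient whose INR or eosinophils become abnormal after the triggering draw while bilirubin stays at or below 2xULN and none of the listed clinical signs appears. In that patient the omitted test is the one that would require withdrawal.

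**Working it through.** No published figure is at issue. The check compares the tests that the rules need with the tests that the panel supplies.

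**Step 1: what each liver rule in 7.8.1 needs, and what the Section 7 panel gives.**

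| Rule | Needed beyond ALT/AST | Supplied by the 72-hour minimum |
|---|---|---|
| ALT/AST >8xULN | nothing | fully judgeable |
| ALT/AST >5xULN for more than 2 weeks | nothing | fully judgeable |
| ALT/AST >3xULN with TBL >2xULN or INR >1.5 | TBL, INR | TBL yes, INR no |
| ALT/AST >3xULN with clinical signs and/or eosinophilia >5% | six clinical signs, eosinophils | signs by clinical assessment; eosinophils no |

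The six signs are fatigue, nausea, vomiting, right upper quadrant pain or tenderness, fever and rash.

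**Step 2: count.** Laboratory criteria beyond ALT/AST in the third and fourth rules: {TBL, INR, eosinophils} = 3. Named panel: {ALT, AST, TBL, ALP, GGT}. Overlap: {TBL}, so 1 of 3 is covered. With INR and FBC with differential added, the overlap is {TBL, INR, eosinophils}, so 3 of 3 are covered. Two of the four liver rules are affected, each in one alternative limb.

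**Step 3: can another section supply the missing tests?**

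- *The triggering draw.* A routine draw under the full Section 7 list includes INR and the differential, so both limbs can normally be judged at that moment. They cannot be judged again on a minimum-panel repeat.
- *Section 7.7.* If the repeat is handled as an unscheduled visit, the required FBC and LFT bring in both tests and nothing is missing. Section 7 speaks of monitoring on a routine schedule and at unscheduled visits. The list in 7.1 includes "Withdrawal visit, Unscheduled visits, Participant withdrawal and at CAS closure", and Table 9.1 gives the time points for lab results as "Screening, monthly, quarterly, unscheduled". An off-schedule repeat therefore plausibly counts as unscheduled, but no section says so. If it does, the protocol gives two different minimum panels for the same event.
- *Blood draws apart from a clinic visit.* Table 9.1 has lab results monthly, while 7.4 says "Monitoring activities may be conducted via phone at 4 weeks and 8 weeks after the baseline". Blood taken without a clinic attendance is therefore foreseeable in this scheme. The 7.7 minimum includes weight and height, which presumes attendance in person.

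**Result.** The gap is confined to a repeat that is a blood draw only, is not treated as a 7.7 visit and is drawn to the stated minimum.

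**The case against.** The strongest reply is that the protocol, read as a whole, already covers the case. The sentence sets only a minimum. The next paragraph sends the prescriber to the rules that name INR and eosinophilia. The protocol names no stand-alone blood draw, so an off-schedule repeat reads naturally as an unscheduled visit with FBC and LFT. The waiver moves procedures to a local site, and nothing says that it reduces them. The monthly draws that accompany phone contacts are routine draws under the full list and do not define the content of the 72-hour repeat. The rules are not tied to the repeat sample either, and both limbs can normally be judged on the triggering draw. Finally, 7.8.1 has other mandatory grounds for withdrawal: the prescriber's judgement on safety or best interests, and the development of a condition listed in the exclusion criteria, which include clinically significant coagulation and hepatic abnormalities.

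Most of this stands, and it makes the gap narrow. It does not close it. A minimum defines what counts as compliance. The reference to 7.8.1 shows that the panel is meant to serve those rules, but it adds no test. No section states that the repeat is a 7.7 visit. The triggering draw cannot show a change that comes after it, and the purpose of a repeat is to see how the injury develops. The other grounds rest on clinical judgement, and a prescriber cannot weigh an INR that was not measured. The waiver and the phone contacts are only examples of how a blood-only repeat could arise; the protocol does not describe that case.

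**Conclusion.** The concern holds as a small inconsistency in safety monitoring, at the level of something to consider. On the Section 7 sentence alone, the repeat panel covers 1 of the 3 laboratory criteria that the two compound rules use beyond ALT/AST. One alternative limb in each of two mandatory rules cannot be judged on that sample. The bilirubin limb, the six clinical signs and the two ALT/AST-only rules are unaffected.

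The conclusion rests on two conditions: the repeat is a blood draw not handled under 7.7, and the site stops at the stated minimum. The protocol does not give how often either happens, or how often INR or eosinophils alone would meet a rule, so no frequency and no delay are claimed. Appendix 3, the monitoring schedule, is not shown and may say more. No statistical figure is affected.

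**What to change.** In Section 7, change the 72-hour panel to: repeat ALT/AST, total bilirubin, alkaline phosphatase, GGT, INR, and FBC with differential, wherever the sample is drawn. The thresholds in 7.8.1 stay as they are and remain with the sponsor's clinical team.

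The cost is a few words in one sentence and two tests at a draw already required, assumed to mean one or two extra tubes. Both tests are already on the routine Section 7 list. Every repeat need not be declared a full 7.7 visit, which would add five further items: weight, height, EUC, AED plasma levels and notification of the Project Office. With the change, all 3 laboratory criteria can be judged on every repeat, and INR and the differential no longer depend on whether the repeat counts as a 7.7 visit.
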